### 3.4c. Smoking Measures

We will obtain smoking measures at intake and also on the PET scan day, which may include the following.

1. Fagerstrom Test for Nicotine Dependence (FTND).(31) This will be used to measure the severity of nicotine dependence. It is a 6-item scale with an internal consistency of .61 and its total score is closely related to biochemical measures of intensity of smoking.

2. Smoking History. This questionnaire will assess basic smoking status and history such as number of years smoked, number and length of quit attempts, reasons for quitting, and second hand smoke exposure.

3. Nicotine Withdrawal Checklist.(32) This measures the severity of eight withdrawal symptoms on 5-point Likert scales.

4. Tiffany Questionnaire of Smoking Urges (QSU).(33) The QSU-brief is a 10-item questionnaire that evaluates the structure and function of smoking urges. Subjects indicate on a likert-type scale how strongly they agree or disagree with each statement with a score of 1 (strongly agree) to 7 (strongly disagree). This characterizes ‘urges to smoke’ into a negative affect related to relief of withdrawal symptoms and positive affect related to expectancy of reinforcement.

### **3.4d Cognitive Measures**

We will obtain these measures at baseline and up to two times on the PET days.

**1. Cogstate Battery:** This computerized test battery will assess memory and cognition. The tasks may include:

- a. International Shopping List Task – a computerized task to assess verbal learning and memory.
- b. Groton Maze Learning Task – a computerized task to assess executive function and spatial problem solving.
- c. Detection Task – a computerized task to assess psychomotor function and speed of processing.
- d. Identification Task – a computerized task to assess visual attention and vigilance.
- e. One Card Learning Task – a computerized task to assess visual learning and memory.
- f. One Back Task – a computerized task to assess attention and working memory

**2. Probabilistic Reward Task:** The PRT has been successfully used to assess reward responsiveness (166-168). In each trial, subjects choose which of two difficult-to-differentiate stimuli was presented. Stimuli consist of simple cartoon faces (diameter: 25 mm; eyes: 7 mm) presented in the center of the monitor. At the beginning of the trial, the face has no mouth. After a given delay, either a straight mouth of 11.5 mm (“short mouth”) or 13 mm (“long mouth”) is presented for 100 ms. Subjects are instructed to press an appropriate button to decide whether a long or small mouth had been presented. Unbeknownst to subjects, correct identification of one stimulus (“rich stimulus”) is rewarded three times more frequently (“*Correct! You won 20 cents*”) than the other (“lean”) stimulus. In healthy controls, this reinforcement schedule leads to a response bias (i.e., a preference for the more frequently rewarded stimulus). The degree of response bias toward the more frequently reinforced alternative will be used for operationalizing sensitivity to reward.

**3. Cold Pressor Task:** Subjects may be asked to participate in the Cold Pressor Task. The cold pressor task (CPT) is a stress task used to measure pain sensitivity and pain tolerance. This task will be used to determine alterations in pain thresholds as a result of nicotine use. Participants will immerse their hand (up to the wrist) for up to 3 minutes in the experimental (ice-cold temperature 0-4°C) and control (room temperature (20°C)) conditions. Physiological measure (heart rate, blood pressure and subject responses (stress, mood) will be collected 5 minutes before, 1 minute into, and immediately after the CPT.

### 3.5 Experimental Methods

#### MRI.

Within approximately 6 months of the PET study, anatomical MRIs will be acquired at the Yale University MRI Center. Subjects will be taken through a ferromagnetic metal detector before entering the scan room. The purpose of the MRI scan is to direct the region of interest placement on the lower resolution PET images. The T1 weighted images will be acquired on a 3 Tesla Siemens Scanner. There will also be an additional resting state scan with subjects in the scanner, eyes open, fixating on a cross. Smokers who participate in the 2-8 week PET scan set may return to have a second MRI with resting state at 2-8 weeks withdrawal. A member of the research team will accompany the subject and remain for the duration of the scan.

Prisma Scan sequence: 64 Channel

Series 1: 3 plane localize

Series 2: Sag 3d tfl; 256fov; 1mm thick slices; 176 slices total; TE 2.77; TR 2530; TI 1100; FA 7; 256X256 1 average.

Series 3: Resting state: Ep2d bold; 210fov; 2.5mm thick slices; TE 30; TR 3400; FA 85; 84x84 (Run twice).

Series 4: Diffusion Tensor Imaging (DTI) sequence

MR images provide a matching anatomical atlas for creating individualized region-of-interest templates for each subject. We will also examine functional connectivity at rest.

#### Amphetamine challenge

Dextroamphetamine sulfate is the dextro isomer of the compound d,l-amphetamine sulfate, a sympathomimetic amine of the amphetamine group. It is an FDA approved drug available for the treatment of narcolepsy and attention deficit hyperactivity disorder (maximum approved total daily dose of 5-60 mg). After the first [C]PHNO scan, dextro-amphetamine (0.5 mg/kg, PO) will be given in increments of 5 or 10 mg, as it is available in 5 mg and 10 mg tablets, and will be rounded down to approximate 0.5 mg/kg total dose without exceeding it. Total dextro-amphetamine dose will not exceed 50 mg per scan. A second transmission and emission scan will be acquired approximately 2.5-3 hours post amphetamine identical to the methods outlined previously. The timing of the second [C]PHNO administration and subsequent PET scanning (i.e., 2.5-3 hours) corresponds to the time of maximum plasma concentration of amphetamine as stated in the respective FDA-approved product labeling. EKG and frequent BP monitoring will occur throughout the study and until the vital signs are within normal limits. Supplemental oxygen will be provided via nasal cannula if necessary. If the systolic BP reaches or exceeds 200 mmHg for more than 5 minutes, the study doctor will take the appropriate clinical measures in order to lower the BP, which may include phentolamine administration (5 mg IV over 10 min) or other appropriate measures.

Following the post-amphetamine PET scan, subjects will be assessed (EKG and vital signs) by one of the research nurses. Subjects will be discharged when vital signs are within normal limits

and when behavioral changes (if any) are found to be not clinically significant by the MD attending to the subject at the PET Center. If subjects experience any adverse events, they will be treated until they become asymptomatic, prior to discharge.

Behavioral response to amphetamine will be measured by self-ratings with a simplified version of the Amphetamine Interview Rating Scale (van Kammen and Murphy, 1975). Four items will be investigated: euphoria ("feel good"), alertness ("feel energetic"), restlessness ("feel like moving") and anxiety ("feel anxious"). Self-ratings will be obtained by analog scales at the following times relative to the d-amphetamine administration: -5 minutes, 0, and hourly thereafter until end of the second scan.

## **PET**

PET scans may be performed on the High Resolution Research Tomograph (HRRT, 2-3 mm resolution) or another similar camera. Venous catheters will be used for i.v. administration of the radiotracers, venous blood sampling of activity, and for venous blood sampling of amphetamine plasma levels and hormone levels. At the beginning of scan, the subject's head will be immobilized and a transmission scan will be obtained for attenuation correction. PET scans will be acquired using bolus or bolus to infusion administration of up to 10 mCi of [C]PHNO and subjects will be scanned for up to 2 hours. Dynamic images of radioactivity concentration are reconstructed with corrections for attenuation, normalization, random events, scatter, and deadtime. Subject motion is corrected automatically on an event-by-event basis with the Vicra motion tracking system. Vital signs (blood pressure, pulse and respiration) are collected prior to and during each PET scan. Urine pregnancy test will be again administered on the PET scan day prior to the initiation of any imaging procedures. Smoking abstinence, when appropriate, will also be confirmed for smoking subjects prior to PET scanning.

PET scanning will then proceed as following for each aim:

Aim 1. Smoking subjects will be asked to come in for two [C]PHNO scans with amphetamine administration. The first scan will be during the first 2 weeks of withdrawal with the option to come back again at 2-8 weeks of withdrawal. Nonsmoking subjects will be asked to come in for one set of two [C]PHNO scans with amphetamine administration. Up to 10 mCi of PHNO will be administered per scan. After the first scan, subjects will take amphetamine (0.5mg/kg) by mouth, and then will be imaged again with PHNO. If technical difficulties arise, the second PET scan of the set may have to be re-scheduled and will be scheduled as soon as possible. In that case, subjects may be asked to re-take amphetamine on the day of the rescheduled PHNO scan, approximately 3 hrs prior to the scan. Amphetamine dose will not exceed 50mg per scan. Subjects will not be allowed to drive home.

In the rare event that a scan would fail post injection, subjects may repeat each scan set up to a total of 8 PHNO scans for smokers and 4 PHNO scans for nonsmokers.

### **3.6 Image analysis.**

The primary outcome measure is the binding potential ( $BP_{ND}$ ), which in turn is proportional to the available receptor concentration ( $B_{avail}$ ), given that there is no change in affinity ( $K_D$ ) and that nondisplaceable (nonspecific and free) uptake does not differ between subjects and studies. We will examine the regions-of-interest listed below with the cerebellum used as a reference region because it is devoid of  $D_{2/3}$  receptors.

We obtain an MRI (as previously described) to use as a guide to place our regions of interest. This is because we can define anatomical regions of interest on the MRI, which provides structural information and then we can apply these regions of interest to the PET scans. The PET scans alone are not sufficient to identify brain regions. The PET image sets are aligned and resliced to yield images in the same planes and spatial system as the MRI images using AAL template. Primary ROIs will be caudate, putamen, ventral striatum, globus pallidus, and substantia nigra. Cerebellum will be the reference region.

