**Imaging amphetamine-induced DA release in smokers vs. nonsmokers measured with [C]PHNO and PET.** Amphetamine administration results in a reliable and robust increase in extracellular DA and has been widely used in brain imaging studies as a marker of DA function in psychiatric and healthy populations(8, 9, 12-16). We have chosen oral amphetamine based on its robust and reliable DA signal and because it is routinely used in PET studies(17-23) and by our group to probe DA neurotransmission. The amphetamine robustly increases synaptic levels of DA. The increased DA competes with the radiotracer to bind at the DA receptor, thus an increase in DA results in a decrease in radiotracer binding compared to baseline. This allows calculation of the “occupancy” of the receptors by DA or a change in binding potential (BP), and is an indirect measure of DA release based on the “occupancy model”(13). We have obtained preliminary data that demonstrates blunted DA release in smokers at 2-3 weeks of abstinence vs. controls and is similar to what has previously been found in cocaine- and alcohol- dependent individuals(8, 9). While the previous studies(8, 9) used [C]raclopride which measures striatal D2/3 receptor binding, we propose to use [C]PHNO which measures striatal and extrastriatal (substantia nigra and globus pallidum) D2/3 binding(24). Importantly, blunted DA release in cocaine-dependent individuals was associated with the choice to self-administer cocaine over money(8) and with treatment failure(10). In the current study, we will determine whether smokers have blunted DA release compared to nonsmokers and if the degree of DA release in smokers is associated with time to relapse.

**3. Research Plan:** Summarize the study design and research procedures using non-technical language that can be readily understood by someone outside the discipline. Be sure to distinguish between standard of care vs. research procedures when applicable, and include any flowcharts of visits specifying their individual times and lengths.

**3.1 Overall plan for Aim 1: To determine amphetamine-induced DA release in nonsmokers and tobacco smokers during acute and prolonged nicotine withdrawal.** We will image up to 50 smokers and 40 nonsmokers.

**Smoker-subjects:** Subjects that qualify for the study will be asked to participate in the following:

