### 3.7 Statistical analysis.

Demographics between smokers and nonsmokers will be compared using  $t$  tests or Chi-Square tests, as appropriate. Scores on psychological tests such as depressive symptoms at baseline will be compared between groups and may be used as covariates in subsequent analyses. All outcomes will be summarized descriptively and assessed for normality prior to analysis using normal probability plots and Kolmogorov test statistics. Transformations or nonparametric analyses will be performed as necessary. All tests will be two-sided and considered statistically significant at  $\alpha = 0.05$ . Post-hoc comparisons will be conducted as necessary with significance levels adjusted for multiple comparisons basing the adjustment on the number of conceptually related statistical tests within each hypothesis. All statistical analyses will be conducted using SAS version 9.3 (Cary, NC).

**Aim 1. To determine if amphetamine-induced DA release is blunted during abstinence in tobacco smokers compared to nonsmokers.** Hypothesis 1. We hypothesize that amphetamine-induced striatal DA release will be blunted in smokers compared to nonsmokers. Power Calculations for Hypothesis 1: Our preliminary data revealed blunted amphetamine-induced DA release ( $d=0.91$ ) in the ventral striatum among smokers ( $-21\% \pm 12.0$ ) compared to nonsmokers ( $-29\% \pm 6.3$ ). Assuming a two-sided  $t$ -test with  $\alpha=0.05$ , 40 nonsmokers and 50 smokers assessed after 14-21 days of abstinence will provide 80% statistical power to detect effect sizes as small as  $d=0.63$ , which compares favorably with the effects observed above.

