Regional [ $^{11}\text{C}$ ]PHNO uptake for each subject will be quantified as  $\text{BP}_{\text{ND}}$  described above for each ROI and will represent the primary outcome measure for the proposed experiments. Repeated measures ANOVA will be used to evaluate the change between scans ( $\Delta\text{BP}$ ) for brain measures for the scans.  $\Delta\text{BP}$  will be computed as  $[(\text{BP}_{\text{baseline}} - \text{BP}_{\text{condition}}) / \text{BP}_{\text{baseline}} \times 100]$ . Analysis will be conducted using SAS version 9.1 (Cary, NC).  $N=20$  subjects per group is necessary to detect differences between smokers and nonsmokers. Potential associations, e.g., relationship between magnitude of dopamine release and time to relapse, will be examined using correlation analysis with Type I error corrected for multiple comparisons. Exploratory analyses of the other cognitive and behavioral measures and their relationship to relapse will also be performed.

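### PHNO protocol: five primary regions and a primary outcome of BPND, but no single ΔBP test named to decide a hypothesis about striatal dopamine release

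*Combined protocol and SAP*

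**What the plan says.** All references are to the PHNO protocol, the second of the two protocols in the combined document.

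- **Outcome.** Section 3.6, Image analysis: "The primary outcome measure is the binding potential", meaning BPND. Section 3.7 repeats that BPND is quantified "described above for each ROI and will represent the primary outcome measure for the proposed experiments". Section 11, Statistical Considerations, carries the same sentence.
- **Regions.** Section 3.6: "Primary ROIs will be caudate, putamen, ventral striatum, globus pallidus, and substantia nigra".
- **Hypothesis 1.** Section 3.7: "We hypothesize that amphetamine-induced striatal DA release will be blunted in smokers compared to nonsmokers". No region is named.
- **Anatomy.** The Background in Section II describes the tracer as one "which measures striatal and extrastriatal (substantia nigra and globus pallidum) D2/3 binding". It also explains that release is inferred from the fall in binding relative to the baseline scan.
- **Planning data.** Section 3.7 gives a pilot effect of d=0.91 "in the ventral striatum among smokers" (−21%, SD 12.0) against nonsmokers (−29%, SD 6.3). It then gives 80% power at d=0.63 for one two-sided t-test at 0.05 with 40 nonsmokers and 50 smokers.
- **Analysis.** Repeated measures ANOVA of the change between scans, with ΔBP defined as the percentage fall from baseline. No region factor, group-by-scan term or deciding effect is stated.
- **Error control.** "All tests will be two-sided and considered statistically significant at" 0.05. Sections 3.7 and 11 attach a multiplicity adjustment to post-hoc comparisons, sized by the number of related tests within a hypothesis. A separate correction covers the correlation analyses.

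**The concern.** The named primary outcome and the hypothesis do not line up, either in measure or in region. BPND indexes available receptors at one scan; release is a difference between two scans. Five regions are primary, yet two lie outside a striatal hypothesis by the protocol's own description, and only one has planning data. Nothing says whether a difference in one region, some or all of them is needed, or whether a striatal composite or an ANOVA term decides.

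Without such a rule, a nominal result in any single region, even an extrastriatal one, could be presented as confirming blunted release. The power statement, meanwhile, presupposes one test that the protocol never identifies.

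**Working it through.** **1. Inputs.** Group sizes 40 and 50, two-sided 0.05, d=0.63 and d=0.91, and N=20 per group (Section 3.7); five primary regions (Section 3.6). The documents give no correlations between regions, so 0, 0.5, 0.7 and 0.9 are assumed.

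**2. The plan's own figure.** For a two-sample t-test the noncentrality is d × √(n1·n2/(n1+n2)). With 40 and 50, √(2000/90) = 4.714, so at d=0.63 it is 2.970 on 88 degrees of freedom, against a critical value of 1.987. Power is 83.6%. The effect detectable with 80% power is d=0.60. The stated 80% at d=0.63 is thus slightly conservative; 36 versus 45 subjects (10% loss) would give a detectable d of 0.634, but no such loss is stated. The protocol's second figure, N=20 per group, gives 80.1% at d=0.91. Both figures fit one test at 0.05.

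**3. Pilot effect.** The printed means and SDs, with equal weights, give 8/√((12.0² + 6.3²)/2) = 8/9.58 = 0.83. Reaching 0.91 would need unequal pilot groups, whose sizes are not given.

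**4. Testing every primary region at 0.05.** With no true difference and independent regions, the chance of at least one significant result in either direction is 1 − 0.95⁵ = 22.6%. In the blunted direction only it is 1 − 0.975⁵ = 11.9%. With equal pairwise correlation:

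| Assumed correlation | Either direction | Blunted direction only |
|---|---|---|
| 0 | 22.6% | 11.9% |
| 0.5 | 18% | 9% |
| 0.7 | 15% | 7% |
| 0.9 | 10% | 5% |

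The single-test references are 5% and 2.5%.

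**5. Adjusting instead.** Bonferroni over five regions sets alpha at 0.05/5 = 0.01; over three striatal regions, 0.05/3 = 0.0167. With 40 versus 50, by noncentral t:

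| Tests | Power at d=0.63 | Power at d=0.91 |
|---|---|---|
| One | 83.6% | 98.9% |
| Three | 70.1% | 96.6% |
| Five | 63.2% | 94.9% |

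At d=0.83, five-way adjustment leaves 90%. At N=20 per group and d=0.91 it leaves 57.0%, against 80.1% for one test.

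**The case against.** **The measure is already right in substance.** Directly after calling BPND primary, Section 3.7 says the ANOVA evaluates the change between scans and gives the ΔBP formula. BPND is what is measured and ΔBP is how it is analysed. This stands. A reader might infer that a smoker–nonsmoker difference in BPND at a single scan would count as a primary result, but the documents plan no such test. What remains is a labelling fault that should be corrected.

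**Multiplicity is partly covered.** After an ANOVA, regional follow-ups could reasonably be called post-hoc comparisons, which would bring them under the adjustment. That reading is possible, but the sentence does not say it, the regions are prespecified as primary, and no method or decision rule follows from it.

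**Power survives.** A reader might infer from the 63% that the design fails once five regions are adjusted for. The documents do not support that. d=0.63 is given as the smallest detectable effect and 0.91 as the observed one, and at 0.91 power with 40 versus 50 stays at about 95%. Bonferroni is also conservative for correlated regions.

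**The 22.6% overstates the harm.** It counts both directions and assumes independence. Only about half concerns false support for blunting, and correlation lowers it further. This stands, so the whole range should be given.

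**Five regions have a rationale.** Extrastriatal sensitivity is part of the case for this tracer, and the hypothesis in the Aim 1 statement is not limited to striatum. That justifies measuring these regions. It does not settle which one decides Hypothesis 1.

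**Conclusion.** The concern holds as a missing decision rule. The protocol makes BPND in five regions primary, while the hypothesis it powers is about striatal ΔBP and the only planning data are for ventral striatum. If each primary region were tested at 0.05, the familywise error would be about 10% to 23% in either direction, or about 5% to 12% in the blunted direction. These ranges rest on assumed equal correlations between 0 and 0.9 and on any one region sufficing, a rule that the protocol neither states nor excludes. Full adjustment lowers power from 84% to 63% at d=0.63 but leaves 95% at d=0.91, so lost power is secondary. This should be corrected before group data are analysed; it does not invalidate the design.

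**What to change.** In Sections 3.6, 3.7 and 11 of the PHNO protocol:

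1. State that Hypothesis 1 is decided by one test at two-sided 0.05: the smoker–nonsmoker difference in ΔBP in the ventral striatum. This is the only region with planning data, and it matches the single-test power statement. One prespecified whole-striatum ΔBP would also fit the hypothesis, but it has no planning data.
2. State the sign of ΔBP. The formula makes a fall in binding positive, whereas the pilot figures are printed as negative.
3. Make ΔBP in caudate, putamen, globus pallidus and substantia nigra secondary, and say explicitly that the Section 3.7 multiplicity adjustment applies to them.
4. Make baseline BPND descriptive.
5. Name the smoker scan set used in the deciding test. First reconcile the Aim 1 statement and the PET section, which place the first set within two weeks of abstinence, with the power paragraphs in Sections 3.7 and 11, which assume 14–21 days. The sponsor must settle which applies.

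The cost is wording plus that timing decision; the naming of the test itself needs no extra subjects or scans. The downside is that a finding confined to another region could no longer be called primary.
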